#### 8.8 ECHOCARDIOGRAM EVALUATION

Echocardiograms will be evaluated as described in the Echo Protocol (Section 17.8).

#### 8.9 MISSED SUBJECT VISITS

The Investigator(s) will make every attempt to follow the subjects and subjects will be encouraged by the Investigator(s) to report any address or telephone number changes to the implanting site. They will also be informed of the importance of returning for scheduled follow-up visits even if they are not having any problems.

If a subject cannot be reached for a follow-up visit, the Investigator will document on the CRF, the efforts undertaken to contact the subject or the subject's primary health care provider. These efforts should include 3 attempts of telephone contacts at separate dates and times, and a registered letter before the end of the follow-up window. If a subject cannot be reached for the follow-up visit and misses the scheduled visit, the visit will be recorded as a missed visit on the date of last attempted contact. Subjects who miss a visit will not be considered withdrawn. At the next visit interval, the Investigator and/or designee will attempt to contact the subject again for follow-up. Should this attempt to contact the subject fail, a family member should be contacted in addition to the subject. Subjects who miss 2 sequential follow-up visits will be considered lost to follow-up at the second missed visit and exempt from future study follow-up visits. After the subject is terminated from the study, the Investigator will attempt to determine if the subject is alive, including searching national mortality registries as permitted by local laws.

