### 3.3 BENEFITS

As mentioned above, the size 23 mm Magna mitral valve is one size smaller than the size 25 mm Magna mitral valve approved by FDA in August 2008. The size 23 mm Magna mitral valve would be implanted in same size mitral annulus as the size 27 mm porcine Carpentier-Edwards Duraflex mitral low pressure valve, model 6625LP. The Duraflex valve was approved by FDA in September 1991.

Based on Edwards implant data, 29% of model 6625LP bioprostheses implanted from 1991 to 2004 were size 27 mm. The availability of the size 23 mm Magna mitral valve would directly benefit these patients by offering the long-term durability of a pericardial valve.

There are no guaranteed benefits from participation in this study. Study subjects may benefit from participation and it is possible that future subjects may benefit based upon the results of the study.

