## 5 STUDY DESIGN

This is a prospective, non-randomized, multi-site descriptive study. A minimum of 15 and up to 20 subjects will be implanted at a minimum of 2 and up to 8 participating investigational sites, within the US and internationally. Subject participation will last for 5 years. Subjects will be assessed for clinical follow-up at the following intervals: pre study procedure, at implant, index hospitalization discharge or within 30 days of implant, whichever comes first, 6 months post

procedure, 1 year post procedure, and annually thereafter until 5 years post procedure or death, whichever occurs first.

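### Section 8.9 ends scheduled follow-up after two consecutive missed visits and writes no way back, although late safety rates are planned over 5 years

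*Combined protocol and SAP*

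**What the plan says.** Section 5 plans visits at 6 months, at 1 year and then "annually thereafter until 5 years post" procedure, or until death. Section 8.9 adds an earlier end:

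- One missed visit does not end participation: "Subjects who miss a visit will not be considered withdrawn".
- Contact effort is specified: "These efforts should include 3 attempts of telephone contacts at separate dates and times, and a registered letter before the end of the follow-up window". When contact also fails at the next interval, a family member is to be contacted.
- After the second consecutive miss, the subject is "considered lost to follow-up at the second missed visit and exempt from future study follow-up visits".
- What remains is a vital-status check: "After the subject is terminated from the study, the Investigator will attempt to determine if the subject is alive, including searching national mortality registries", where local law permits.

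The withdrawal grounds in section 6.4 are withdrawn consent, conflict with the subject's medical treatment, and participation in another investigational study. Missed visits are not among them.

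Sections 4.1 and 11.1.1 list 14 safety endpoints, with late rates by Kaplan-Meier and per cumulative patient-year. The Analysis Population text in section 11 includes all implanted subjects and their data up to explant or death. It does not say when a lost subject is censored.

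**The concern.** A subject can leave the study without withdrawing consent and with the valve still in place. After exit, the alive-or-dead check informs one of the 14 endpoints, death. It does not show whether a death was valve-related. It also does not detect thromboembolism, thrombosis, hemorrhage, perivalvular leak, endocarditis, hemolysis, structural deterioration, non-structural dysfunction, reoperation or explant.

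Two things are at stake. The first is precision, because 15 to 20 subjects give few patient-years. The second is possible informative censoring. A subject may miss visits because of illness or because a valve problem was treated elsewhere, and Kaplan-Meier censoring does not correct for that. The documents do not show that this happens, but the rule prevents the study from finding out once contact is restored.

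**Working it through.** The plan has no loss, dropout, power or event figure to reproduce, so the check applies the rule to the stated schedule.

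**Inputs.** Visits at 6 months and 1, 2, 3, 4 and 5 years (section 8.7.3). Windows from Table 6: months 3 to 6 for the first visit, ±1 month at 1 year, ±2 months at later years, so they close at months 6, 13, 26, 38, 50 and 62. Cohort of 15 to 20 and 5 years of participation (section 5), so the maximum is 15 × 5 = 75 to 20 × 5 = 100 patient-years (PY).

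**Step 1: follow-up forgone.** Exit is taken at the close of the second missed window. Section 8.9 dates a missed visit at the last attempted contact, so exit could be slightly earlier. Months forgone = 60 − closing month, or 0 if the window closes after month 60. PY = months / 12.

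| Missed pair | Exit (month) | Months forgone | PY | Share of 75 PY | Share of 100 PY | Later visits forgone |
|---|---|---|---|---|---|---|
| 6 months + 1 year | 13 | 47 | 3.9 | 5.2% | 3.9% | 4 |
| 1 + 2 years | 26 | 34 | 2.8 | 3.8% | 2.8% | 3 |
| 2 + 3 years | 38 | 22 | 1.8 | 2.4% | 1.8% | 2 |
| 3 + 4 years | 50 | 10 | 0.8 | 1.1% | 0.8% | 1 |
| 4 + 5 years | 62 | 0 | 0 | 0% | 0% | 0 |

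These are per-subject ceilings. They assume that the subject is reached at once and stays to year 5.

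**Step 2: precision.** With no events, the one-sided 95% upper bound on a late rate is −ln(0.05)/PY = 2.996/PY. Assume 1, 2 or 3 subjects exit at the 1-year date, each forgoing 4 PY (nominal visit dates).

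- n = 15: PY falls from 75 to 71, 67 or 63, and the bound rises from 3.99 to 4.22, 4.47 or 4.76 % per PY.
- n = 20: PY falls from 100 to 96, 92 or 88, and the bound rises from 3.00 to 3.12, 3.26 or 3.40 % per PY.

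The loss of precision is modest.

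**Step 3: an uncollected event.** Suppose two events occur in the cohort and one subject is lost at 1 year.

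- One event falls in the lost time, n = 15: observed 1/71 = 1.41 % per PY, against 2/75 = 2.67 % in truth. For n = 20: 1/96 = 1.04 %, against 2/100 = 2.00 %.
- Neither event falls in the lost time: observed 2/71 = 2.82 % (n = 15) or 2/96 = 2.08 % (n = 20).

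If events fall evenly over time at risk and loss is unrelated to them, the expected observed count for n = 15 is 2 × 71/75 = 1.893, and 1.893/71 = 2.67 %. The average is therefore correct. A downward bias needs events to be more likely in the lost time than elsewhere.

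**Step 4: time before exit.** Step 3 assumes that unobserved time is not counted as event-free. A subject who misses the 6-month and 1-year visits was last seen at discharge or within 30 days of implant. Censoring at the second missed visit would credit up to about a year with no event ascertainment. Section 11 does not say which date applies.

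**The case against.** Several points on the other side stand.

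- The trigger is not casual. Calls, a registered letter and family contact are expected first, and one miss is expressly not a withdrawal. Section 8.7.2 has seasonal absence recorded so that visits can be planned around it, and collects alternate contacts, so ordinary travel is not a fair example of how subjects would be lost.
- A reader might infer that the study needs every late valve event. The documents do not support that: section 5 calls the study descriptive, and there is no hypothesis, event target or performance goal. Section 3.3 names "offering the long-term durability of a pericardial valve" as a benefit, with citations, not as an endpoint here.
- A reader might take 47 of 60 months (78%) as the typical loss. It is the worst of five cases, and the last case costs nothing.
- A reader might infer that late rates will be understated. Step 3 shows that this needs loss related to events, which is plausible but undocumented.
- Both listed effectiveness endpoints (EOA and NYHA class) are at 1 year. The earliest exit is the missed 1-year visit itself, so the rule cannot cost them.

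It can also be said that exemption only lifts a duty, and that other sections keep data flowing: interim visits and outside-physician information (8.7.3), explant reports (10.4.2), and a final assessment at study termination (8.10). No text forbids accepting data from a subject who returns. However, section 8.9 also calls the subject terminated, and none of those sections clearly reaches a terminated subject. A site could reasonably stop collecting.

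**Conclusion.** The point holds as a change that should be made, not as a flaw that defeats the study. Section 8.9 states a rule that ends scheduled follow-up and then seeks only vital status, with no written return path, while late rates for 14 endpoints are planned.

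Per subject, the rule costs at most about 3.9 PY, which is 3.9% to 5.2% of the study maximum, and nothing for the last pair of visits. The effect on precision is small. In a cohort this size, one uncollected event out of two can roughly halve an observed late rate, but whether any bias arises depends on loss being related to events. The total effect cannot be stated, because the documents give neither a loss rate nor a return rate. The counts of lost subjects and events used above are assumptions.

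**What to change.** In section 8.9, replace the permanent exit with the following:

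- A subject who misses two consecutive visits is classed as temporarily lost.
- The contact attempts already defined are repeated at each later annual window through year 5.
- A subject who is reached may resume scheduled visits, including echocardiography and blood work.
- Unless consent is withdrawn, all section 11.1.1 safety events since last contact are collected from the subject, family or treating physician. This includes structural deterioration, non-structural dysfunction and perivalvular leak.
- Final lost status is assigned only at the end of the 5-year window. The vital-status search is kept.

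In section 11, under Analysis Population, add:

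- Subjects never reached again are censored at the last contact with known event status.
- Gap time counts as patient-years only when event status over the gap has been ascertained.
- The number of subjects lost is reported.

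The cost is protocol wording and contact attempts at up to four more annual windows for a few subjects. The downside is some extra site effort. No treatment is affected.

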#### 8.10 CLINICAL STUDY TERMINATION

The Principal Investigator(s) will be notified in writing upon termination of the study. Edwards retains the right to suspend or terminate this clinical study at any time. Safety and review committees associated with the study may recommend termination should safety concerns warrant such action. Upon study termination, the Investigator will contact the study subjects to perform a final follow-up assessment. Subjects should continue seeing their physicians as part of routine clinical follow-up after heart valve replacement surgery.

### 9 DATA COLLECTION AND REPORTING

#### 9.1 DATA COLLECTION METHODS

All required data for this study are to be collected with standardized Case Report Forms (CRFs) for individual subjects; [REDACTED]. The paper CRF forms must be completed, signed by the Principal Investigator or designee and submitted to the Sponsor.

Research coordinators at each clinical site will perform primary data collection drawn from hospital chart and operator worksheet (source document) reviews. CRFs must be kept current to reflect subject status during the course of the study.

Case Report Form Instructions will be provided assist the Investigator(s) and appropriate site staff in the completion of the required CRFs.

#### 9.2 SOURCE DOCUMENTATION REQUIREMENTS

Regulations require that Investigators maintain information in the study subject's medical records that corroborate data collected on the CRFs. In order to comply with these regulatory requirements, all required data for this study is to be recorded in the subject's medical chart for source documentation and data verification as follows:

1. Medical history and physical condition of the study subject before involvement in the study sufficient to verify protocol entry criteria
2. Dated and signed notes in the subject's medical record on the date of entry into the study.
3. Dated and signed notes from each study subject visit with reference to the CRFs for further information, if appropriate (for specific results of procedures and exams).
4. Notations on abnormal lab results and adverse events reported and their resolution.
5. Notes regarding concomitant medications taken during the study.
6. Study subject's condition upon completion of or withdrawal from the study.

### 9.3 QUALITY CONTROL AND QUALITY ASSURANCE PROCEDURES

Because of the potential for errors, inaccuracies, and illegibility in transcribing data into CRFs, originals or photocopies of all relevant procedural records and reports, post-procedural examinations, laboratory and other test results may be kept on file in the Investigator's subject study files. CRFs and copies of test results must be available at all times for inspection by the study monitor.

Data Management personnel will employ a full-featured relational Oracle database on a central server, networked to data entry and data analytical workstations. Conventional data verification sub-routines will be extensively programmed to test entry and logical errors, while all individual (Subject-based) CRFs will be linked for cross-reference. Periodic analysis of each data field (across cases) will be performed in order to examine the expected distributions of data and to identify outliers for possible data entry errors.

## 10 ADVERSE EVENT REPORTING

All types of adverse events (AEs) will be reported by the Investigator and reviewed by the Sponsor in compliance with applicable regulations. Adverse event information will be collected from the point of implant. Adverse event information including but not limited to, a description event, date of onset, and relationship to device will be recorded on the CRF by the Investigator or research coordinator. Adverse events will be followed until they are adequately resolved or explained.

#### 10.1 ADVERSE EVENT

An adverse event is defined as any untoward medical occurrence in a subject or clinical investigation subject administered a product and which does not necessarily have to have a causal relationship with this treatment. An adverse event (AE) can therefore be any unfavorable and unintended sign (including an abnormal laboratory finding, for example), symptom, or disease temporally associated with the use of a medicinal product, whether or not considered related to the medicinal product.

#### 10.2 SERIOUS ADVERSE EVENT

A serious adverse event is defined as any untoward medical occurrence that:

- Leads to death,
- Leads to a serious deterioration in the health of the subject that:
  - Results in life-threatening illness or injury;
  - Results in permanent impairment of a body structure or a body function;
  - Requires inpatient hospitalization or prolongation of existing hospitalization;
  - Results in medical or surgical intervention to prevent permanent impairment to body structure or a body function;
- Leads to fetal distress, fetal death, or a congenital abnormality or birth defect.

All Serious Adverse Events (SAE) must be reported to the Sponsor within one business day of the Investigator becoming aware of the event. **Notification should be done via email to [[contact]](mailto:[contact]) or faxed to [contact].**

SAE reports must include but are not limited to the following information:

- Identifiable subject number;
- Identifiable reporter;
- Adverse event description;
- Date of onset;
- Relationship to device.
- Relationship to procedure

SAEs will be followed until they are adequately resolved or explained. The Investigator(s) will report any SAEs to their local Institutional Review Board (IRB) in accordance with the IRB's requirements.

### 10.3 UNANTICIPATED ADVERSE DEVICE EFFECT

Unanticipated adverse device effect (UADE) is defined in 21 CFR 812 as any serious adverse effect on health or safety or any life-threatening problem or death caused by, or associated with, a device, if that effect, problem, or death was not previously identified in nature, severity, or degree of incidence in the Clinical Investigator's Brochure (Report of Prior Investigations), Clinical Protocol, or Instructions for Use, or any other unanticipated serious problem associated with a device that relates to the rights, safety, or welfare of subjects.

The Investigator(s) will report any UADEs to Edwards Clinical Research within one business day of occurrence or knowledge of the device related event. **Notification should be done via email to [[contact]](mailto:[contact]) or faxed to [contact].** In addition, sites will report all UADEs to their local Institutional Review Board (IRB) in accordance with the IRB's requirements.

UADE reports must include but are not limited to the following information:

- Identifiable subject number;
- Identifiable reporter;
- A description of the event;
- Date of onset;
- Relationship to device.

UADEs will be followed until they are adequately resolved or explained. The Investigator(s) will report any UADE to their local Institutional Review Board (IRB) in accordance with the IRB's requirements.

#### 10.4 DEATHS AND DEVICE EXPLANTS

##### 10.4.1 SUBJECT DEATHS

In the event of subject death, every effort must be made to obtain a copy of the autopsy report and/or death summary. Information on the cause of death and its relationship to the study device will be determined by the Principal Investigator. Copies of available autopsy report and/or a death summary must be sent to Edwards.

If a device is explanted during autopsy, the device should be returned to Edwards for analysis. Return kits for devices will be provided by the clinical monitor upon request.

##### 10.4.2 DEVICE EXPLANTS

In the event a device is explanted, every effort must be made to obtain a copy of the explant procedure report, as applicable. Information on the cause of explant and its relationship to the study device will be determined by the Principal Investigator and recorded. Copies of an available explant report must be sent to Edwards.

Explanted devices should be returned to Edwards for analysis. Return kits for devices will be provided upon request by the clinical monitor.

The explanted valve will be evaluated according to Edwards' quality procedure QCOPG3009: Implantable Products Evaluation Procedure [REDACTED].

## **11 STATISTICAL ANALYSIS**

The safety and effectiveness endpoints of the data obtained from this study will be summarized using descriptive statistics. Safety and effectiveness data for Edwards Lifesciences Carpentier-Edwards PERIMOUNT Plus Pericardial Bioprosthesis, Mitral Model 6900P from Protocol 98-1 will be used to generate a general comparison with the size 23mm Magna mitral valve data from this IDE protocol.

### **ANALYSIS POPULATION**

The primary safety and effectiveness analyses will include all the implanted subjects. All the data collected up to the point of the explant or expirations will be included in the safety and effectiveness analyses.

#### **11.1 SAFETY ANALYSIS**

##### **11.1.1 SAFETY ENDPOINTS**

The following adverse events will be reported for the safety analysis:

- Thromboembolism
- Valve thrombosis
- All hemorrhage
- Major hemorrhage
- All perivalvular leaks
- Major perivalvular leak
- Endocarditis
- Hemolysis
- Structural valve deterioration
- Non-structural valve dysfunction

- Reoperation
- Explant
- Death
- Valve-related death.

Rates of the above referenced adverse events within the early (within 30 days of implant) post-operative period, calculated as the number of events divided by the number of subjects, will be reported.

The calculation of late rates and standard errors for the safety endpoints will be based on actuarial (Kaplan-Meier) methods in addition to rates based on cumulative patient-years.

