mimics the natural saddle shape of the native mitral valve anatomy. The ring is made of waffled silicone-rubber and is covered with a porous polytetrafluoroethylene cloth to facilitate tissue in-growth and encapsulation. Black suture markers on the anterior portion facilitate the orientation of the valve and help avoid obstruction of the left ventricular outflow tract by a strut. The design of the silicone waffle eases needle penetration and provides variable compliance. The waffle has wider cells along the posterior portion, where calcification or irregularities of the native mitral annulus are more frequent. This results in a very compliant sewing ring that facilitates coaptation between the sewing ring and the mitral tissue bed. The width of the sewing ring allows for coverage of an irregular or calcified mitral annulus.

The valve is terminally sterilized in glutaraldehyde and packaged in a sealed jar packaging system consisting of the jar, sleeve, and clip. The finished valve with holder is suspended by a clip and a sleeve within the sealed jar containing glutaraldehyde.

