##### **3.1.2 RISKS ASSOCIATED WITH THE SIZE 23 MM MAGNA MITRAL VALVE**

The following risks, compiled from the literature, are potentially associated with the use of bioprosthetic heart valves include, including the size 23 mm Magna mitral valve:

- Endocarditis
- Fracture of the cobalt-chromium alloy wireform frame
- Malfunctions of the valve due to distortion at implant
- Myocardial infarction
- Prosthesis leaflet entrapment
- Prosthesis nonstructural dysfunction
- Prosthesis pannus
- Prosthesis perivalvular leak
- Prosthesis regurgitation
- Prosthesis stenosis
- Prosthesis structural deterioration
- Prosthesis thrombosis
- Stroke
- Thromboembolism
- Ventricular perforation by stent posts

It is possible that these risks could lead to:

- Reoperation
- Explantation
- Permanent disability
- Death

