##### **3.1.3 RISKS ASSOCIATED WITH MITRAL VALVE REPLACEMENT**

The following risks, compiled from the literature, are potentially associated with mitral valve replacement surgery:

- Angina
- Bleeding
- Cardiac Arrest
- Cardiac arrhythmias, which may include conduction disturbances
- Diabetes,
- Heart failure
- Hemolysis
- Hemolytic anemia
- Hypertension / Hypotension
- Infection,
- Myocardial failure,
- Multisystem organ failure,
- Non-cerebral blood clot
- Pericardial effusion or cardiac tamponade
- Respiratory failure in the chronically ill, debilitated individual,
- Stroke,
- Transient Ischemic Attack
- Ventricular rupture

It is possible that these risks could lead to:

- Reoperation
- Explantation
- Permanent disability
- Death

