#### 11.2.1.1 Hemodynamic Performance

Echocardiography data will be obtained preoperatively, at discharge, 6-months and 1 year, 2 year, 4 year, and 5 year follow-up visits. The echocardiographic hemodynamic parameters to be evaluated are peak gradient, mean gradient, effective orifice area (EOA), EOA index, performance index, cardiac output, cardiac index, left ventricular mass regression (data collected for research; not required for endpoint evaluation), and valvular regurgitation. Descriptive statistics for the continuous echo variables and change from baseline (e.g. mean, standard deviation, and range) categorized by follow up time intervals will be reported. Regurgitation data will be summarized by frequencies at each pre-procedure severity level.

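### Section 11.1.1 reports 14 safety endpoints and plans no summary of all adverse events, so non-fatal events outside the list, including some risks the protocol names, have no planned place in the results

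*Combined protocol and SAP*

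**What the plan says.** Section 11.1.1 opens with "The following adverse events will be reported for the safety analysis" and lists 14 items. The Synopsis and Section 4.1 carry the same 14. The rates are defined on that list: the early analysis covers "Rates of the above referenced adverse events within the early (within 30 days of implant) post-operative period", and for the later period "The calculation of late rates and standard errors for the safety endpoints will be based on actuarial (Kaplan-Meier) methods", with patient-year rates as well. Beyond this, the safety part of Section 11 adds only times to reoperation, explant and death (Section 11.1.1.1, Table 8) and blood data (Section 11.1.1.2).

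The risk sections are wider than the list. Section 3.1.2 includes myocardial infarction and "Ventricular perforation by stent posts". Section 3.1.3 includes "Cardiac arrhythmias, which may include conduction disturbances".

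Collection is also wider. Section 10 states "All types of adverse events (AEs) will be reported by the Investigator", starting from implant, and Table 4 has an item for intraoperative adverse events. The Analysis Population paragraph in Section 11 takes all data up to explant or death into the safety and effectiveness analyses, but names no table, rate or grouping.

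**The concern.** The study is meant to show that a new, smaller size of an approved valve is safe, and Section 3.2 says it will gather data on how complications relate to valve size. A reader of the safety results would expect to learn whether the device risks that the protocol names occurred. For some of them the plan provides no output. If such an event happened and the subject survived without reoperation or explant, the tables could be produced exactly as planned and not show it. If none happened, the tables could not show that either, because an event type that is not tabulated looks the same as one with a count of zero.

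**Working it through.** The documents give no sample-size or power calculation, so there is no stated figure to reproduce. The check compares lists, followed by a short calculation for scale.

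**1. Planned safety outputs.** Section 11.1.1 has 14 endpoints: thromboembolism, valve thrombosis, all and major hemorrhage, all and major perivalvular leak, endocarditis, hemolysis, structural deterioration, non-structural dysfunction, reoperation, explant, death and valve-related death. Early and late rates refer to these. No output is defined for all AEs, for all SAEs, or for events by relationship.

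**2. Section 3.1.2 (15 device risks) against the 14.** The match is read generously: stroke under thromboembolism or hemorrhage; frame fracture, distortion, leaflet entrapment, pannus, stenosis and regurgitation under structural or non-structural valve problems. On that reading 13 risks have a matching endpoint, and 15 − 13 = 2 do not: myocardial infarction and ventricular perforation.

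**3. Section 3.1.3 (18 surgical risks) against the 14.** Bleeding, hemolysis, hemolytic anemia, stroke, transient ischemic attack and non-cerebral clot can be matched, which is 6. The other 18 − 6 = 12 have no clear match, or 11 if tamponade is counted as hemorrhage. Arrhythmia or conduction disturbance is among them.

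**4. Where an unmatched event would go.**

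| Event and course | Planned place in the results |
|---|---|
| Perforation or infarction, fatal | Death, without the cause |
| Perforation leading to reoperation or explant | Reoperation or explant, without the cause |
| Perforation repaired during the index operation, subject survives | Only if it also meets a term such as hemorrhage |
| Non-fatal infarction, no reoperation or explant | None |
| New conduction disturbance, no reoperation or explant | None |

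The last three rows are the gap. The data exist: Section 10 records AEs with device relationship, Section 10.2 adds procedure relationship for SAEs, and Table 4 covers intraoperative events.

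**5. Scale.** Section 5 plans 15 to 20 implanted subjects. One affected subject is 1/20 = 5% to 1/15 = 6.7%.

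The chance of at least one event of a given type is 1 − (1 − p)^n. The documents give no rate p for these events, so the values of p below are assumptions:

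| Assumed p | n = 15 | n = 20 |
|---|---|---|
| 1% | 14.0% | 18.2% |
| 5% | 53.7% | 64.2% |
| 10% | 79.4% | 87.8% |

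If no event is seen, the exact one-sided 95% upper bound is 1 − 0.05^(1/n): 18.1% for n = 15 and 13.9% for n = 20. A zero count is therefore weak evidence, but it is still information that the planned tables would not give.

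**The case against.** The strongest reply is that the list never says *only*, and that the Analysis Population paragraph just above it takes in all collected data. This stands in part: the plan does not forbid an all-AE table. But that paragraph sets a cut-off at explant or death and does not say how events outside the 14 are to be shown. At the least, the two parts need reconciling.

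Other points have some weight.
- Severe cases would be counted under death, reoperation, explant or hemorrhage. This is right, although the cause would not be visible.
- A Data Monitoring Committee member reviews each AE (Section 13.1). That is oversight during the study and not a reported result.
- The Synopsis names an earlier valve approval as a guide for data presentation. Its content is not in the documents, so it may or may not include such a table.
- Thirteen of the 15 device risks have a plausible endpoint, and many unmatched items in Section 3.1.3, such as diabetes or hypertension, are general surgical or medical risks. This limits the point, and separate rows for all of them would add little.

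Three stronger readings are tempting, and the documents do not support them.
- A reader might infer that these events would be absent from the safety results altogether. The first two rows of the table in the working show otherwise.
- A reader might count outflow-tract obstruction as an omitted named risk, because Section 2.3.1 says the suture markers "help avoid obstruction of the left ventricular outflow tract by a strut". It is in neither list in Section 3.1, and it might be classed as non-structural dysfunction; no definition is shown.
- A reader might infer that the outflow-tract (LVOT) echo data have no use, because Section 11.2.1.1 says "The echocardiographic hemodynamic parameters to be evaluated are peak gradient, mean gradient, effective orifice area (EOA), EOA index, performance index, cardiac output" and does not name LVOT assessment. That term is undefined in Tables 3, 5 and 7, and LVOT measurements may feed derived values that are analyzed.

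**Conclusion.** The point holds in a limited form. Section 11 plans no summary of all AEs or all SAEs. Non-fatal events outside the 14 endpoints that lead to neither reoperation nor explant are collected without a planned place in the results, unless they meet another of the 14 terms. This affects two of the 15 named device risks and, among the surgical risks, arrhythmia or conduction disturbance. The study is descriptive with no hypothesis test, so no error rate or sample size is affected; what suffers is the completeness of the safety account.

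The conclusion assumes that endpoint definitions not shown do not bring infarction, perforation or arrhythmia under one of the 14 terms, and that the presentation format cited in the Synopsis does not already require an all-AE table. If either assumption is wrong, the remedy reduces to saying so in Section 11.

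**What to change.** In Section 11.1.1:
- Add a descriptive table of all AEs and all SAEs by type, split into early (within 30 days, including intraoperative) and late, giving number of subjects and number of events. Show device relationship as recorded for AEs, and both device and procedure relationship for SAEs.
- Show myocardial infarction and ventricular perforation as explicit rows, including zero counts. The general surgical risks need no fixed rows, since any that occur will appear in the table.
- Add a sentence reconciling the Analysis Population paragraph with the endpoint list: the 14 endpoints receive early and late rates, and all other events are summarized in the new table.

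The cost is SAP wording and one or two more tables from data already collected. Sample size, visits and conduct do not change. The safety summary may look less favourable.
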